- To test the association between blood lymphocyte counts at baseline, or their precocious ontreatment modifications (T1: 2 weeks after treatment initiation, and T2: before fourth cycle initiation, approximately 12 weeks after treatment initiation) and rwPFS, TTNT-D, TTC-D and OS of HR+/HER2- patients treated with first-line ET plus CDK4/6i;
- To evaluate the association between peripheral blood crude cell counts, namely whole blood cells, neutrophils, monocytes and platelets, as evaluated at baseline and as precocious on-treatment modifications, and patient rwPFS, TTNT-D, TTC-D and OS;
- To evaluate the association between baseline composite parameters, such as the Neutrophil-to-Lymphocyte ratio (NLR), the platelet-to-lymphocyte ratio (PLR), the monocyte-to-lymphocyte ratio (MLR), or the Pan-Immune Inflammation Value (PIV), and patient PFS;
- To evaluate the association between precocious on-treatment modifications (i.e., 2 weeks and ∼12 weeks after treatment initiation) of NLR, PLR, MLR and PIV, and patient PFS;
- To evaluate the association between HER2 status (HER2-low vs. HER2-0; HER2 2+ with negative ISH vs. HER2 1+ vs. HER2-0) in the primary tumor and rwPFS, TTNT-D, TTC-D and OS;
- To evaluate the association between HER2 status (HER2-low vs. HER2-0; HER2 2+ with negative ISH vs. HER2 1+ vs. HER2-0) in one metastatic site (subjected to biopsy before CDK 4/6 inhibitor initiation), and rwPFS, TTNT-D, TTC-D and OS;
- To explore pattern of progression of HR+/HER2- aBC after ET plus CDK4/6i treatment;
- To test the effect on rwPFS, TTNT-D, TTC-D and OS of mastectomy in patients with *de novo* HR+/HER2- aBC.

Study Population

Inclusion criteria:

- Pre- and Post-menopausal patient (woman OR man)
- Age≥18 years
- Diagnosis of aBC. HR+/HER2- aBC, as defined as at least 1% estrogen receptor (ER) and/or progesterone receptor (PgR) positivity at IHC. HER2 negativity is defined on the basis of an IHC score of 0, 1+, or 2+ with absence of gene amplification at in situ hybridization (ISH) analyses.
- Have received or are candidate to receive treatment with palbociclib, ribociclib or abemaciclib in combination with endocrine therapy as first-line treatment for HR+/HER2- aBC.

Exclusion criteria:

- Less than 3 months of follow up from the CDK4/6i start to the date of data cut-off;
- Have received CDK4/6i as monotherapy;
- Have received CDK4/6i as adjuvant treatment for localized disease.

Data collection

The study involves the collection of RWD, i.e. obtained directly from the medical records, electronic or paper, of the patients enrolled in the study. Therefore, no additional patient assessment will be required specifically for study purposes. Data will be collected locally within the center participating in the study, subject to patient consent, and then reported on a platform in .xlsx format.

The types of data collected within this sub-study include:

- Demographic data: date of birth, gender, menopausal status;
- Neoplasm history data: de novo vs metachronous presentation; date of diagnosis of localised disease; prior treatment for localised disease, including type and duration of prior hormonal, chemotherapy and CDK4/6i treatment; number and type of metastatic sites;
- CDK4/6i treatment data: drug used; backbone of hormone therapy and date of initiation of hormone therapy versus initiation of CDK4/6i; use of LHRH analogue;
- Tumor biology data: hormone receptor status, grading, proliferation index at biopsy site of metastasis and, if not available, relative to primary tumor; OncotypeDX;
- Data on haematochemical parameters: complete bloodcounts and some biochemical parameters such as LDH, blood glucose and CA15.3, collected at baseline, 15 days after starting CDK4/6i, after 30 days and at treatment progression;
- Genomic data: genomic alterations available to the patient, performed according to clinical practice; this section includes both somatic mutations and germline DNA alterations.

(2) Toxicity – Comorbidity sub-study

The "toxicity – comorbidity" sub-study aims to add a key piece to the real-world evidence of the three CDK4/6i, allowing for the first time a systematic comparison of the real-world toxicities of palbociclib, ribociclib and abemaciclib.

Objectives and endpoints of the sub-study

Primary objective:

To compare the real-world incidence of severe toxicity, defined as a grade 3 or higher adverse event reported by the clinician, occurring during treatment, among the three CDK4/6i.

Secondary objectives:

- To compare the real-world incidence of overall toxicity, defined as any-grade adverse event reported by the clinician, occurring during treatment, among the three CDK4/6i;
- To assess the incidence of dose reduction conditioning toxicity;
- To assess the incidence of toxicity requiring discontinuation of treatment or switch to another molecule of the CDK4/6i class;

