
Another relevant issue is represented by the potential differential activity of the three molecules across clinical scenarios. In fact, results of published phase III RCTs reported a different magnitude of benefit among clinical settings with three drugs. As an example, in patients with endocrine-sensitive disease, all the three CDK4/6i in combination with ET improve PFS when compared to ET alone. However, only ribociclib

Version 1.1, 01Aug2024

in MONALEESA-2/3/7 trials also improved patient OS in the endocrine sensitive setting, while abemaciclib resulted in not statistically significant OS prolongation in the MONARCH 3 trial, neither OS improvement was observed with palbociclib in the PALOMA-2 trial. In premenopausal women, data from the MONALEESA-7 trial indicate that ribociclib specifically improves PFS and OS in combination with ET in this setting, whereas abemaciclib prolonged PFS and OS in premenopausal women enrolled in the MONARCH 2 trial. 14,18,62 On the other hand, palbociclib resulted in PFS but not OS gain in premenopausal patients form the PALOMA-3 trial. Regarding tumor biology, exploratory analyses from RCTs showed that palbociclib and ribociclib improve PFS in patients with both luminal-A and luminal-B disease, while ribociclib also provided OS benefit in patients with luminal-B disease. 32,33,63 In sub-analyses of the MONARCH 2/3 trials, abemaciclib improved PFS in patients with tumors lacking PgR expression, a feature that contributes to the definition of luminal B-like disease. 20,64 These data suggest a differential activity of the three CDK4/6i drugs in settings that are often encountered during daily clinical practice.

Efficacy of systemic therapies administered on progression to first-line ET+CDK4/6i

While CDK4/6i in combination with endocrine therapy is established as the standard of care treatment for first-line treatment for virtually all HR+/HER2- aBC patients, both in endocrine-sensitive and endocrine-resistant setting, the treatment algorithm for second and subsequent lines for HR+/HER2- aBC is an area of uncertainty. To add a further layer of complexity, the aBC scenario after CDK4/6i is extremely heterogeneous from a biological, genomic and clinical point of view, raising the necessity to find the best treatment pattern at the individual level, based on the combination of patient-specific characteristics.

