- To test the difference in terms of TTC-D between the group of patients receiving ribociclib and palbociclib;
- To test the difference in terms of TTC-D between the group of patients receiving abemaciclib and palbociclib;
- To test the difference in terms of TTC-D between the group of patients receiving abemaciclib and ribociclib;
- To test the difference in terms of rwPFS, TTNT-D and TTC-D among the three CDK4/6i in clinically-relevant subgroups, such as endocrine sensitive and resistant patients, premenopausal women, patients with poorer ECOG PS, patients harboring luminal-B like disease, patients with liver metastases;
- To test the difference in terms of rwPFS, TTNT-D, TTC-D and OS among the three CDK4/6i in older women (defined as >75 years old);
- To test the effect of histology (non special type vs lobular vs other) on rwPFS, TTNT-D, TTC-D;
- To test the difference in terms of rwPFS, TTNT-D, TTC-D and OS among the three CDK4/6i in patients with lobular breast cancer histology;
- To test the difference in terms of rwPFS, TTNT-D, TTC-D and OS among the three CDK4/6i according to disease-free interval (DFI);
- To test the difference in terms of rwPFS, TTNT-D, TTC-D and OS among the three CDK4/6i according to endocrine resistance status, including primary versus secondary resistance;

- To test the difference in terms of rwPFS, TTNT-D, TTC-D and OS among the three CDK4/6i according to different ER expression levels;
- To determine the rwPFS, TTNT-D, TTC-D and OS in the subgroup of patients with brain metastases;
- To determine the rwPFS, TTNT-D, TTC-D and OS in the subgroup of patients with oligometastatic disease and in the subgroup of patients with high metastatic burden;
- To test the effect on rwPFS, TTNT-D, TTC-D and OS of available metabolic biomarkers (e.g. body mass index, glycemia);
- To test the difference in terms of rwPFS, TTNT-D, TTC-D and OS among the three CDK4/6i in patients harboring germline mutations, including *BRCA1*, *BRCA2*, *PALB2*, and in patients with homologous recombination deficiency;
- To test the difference in terms of rwPFS, TTNT-D, TTC-D and OS among the three CDK4/6i in patients harboring genomic somatic alterations, like *PIK3CA* and *ESR1* status;

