continuous variables and the Chi-square and Fisher exact tests for categorical variables. Unpaired t-test will be used to compare numeric variables, at baseline and different timepoints. Classic survival analysis methods will be used to evaluate patient survival outcomes and survival curves will be obtained through the Kaplan–Meier method. Follow-up times will be estimated using the reverse Kaplan–Meier method. Multivariable analysis will be performed through Cox regression modeling to estimate the effects of covariates. To homogenize patients' characteristics among treatment groups, additional adjustment techniques will be eventually used, such as propensity score matching (PSM) and inverse probability of treatment weighting (IPTW). Estimated weights will be then incorporated into a weighted Cox regression model to estimate rwPFS. Area Under the ROC Curve (AUC) values of the models will be calculated using the Caret and pROC R package and compared using Delong's test.

Patients with missing outcome data will be excluded from the analysis. Covariates whose values will be missing in less than 20% were imputed by using the median or the mode value (for numerical or categorical variables, respectively), while covariates with missing values exceeding 20% will be excluded from the present analysis. 90 All statistical tests will two-tailed, and a p value (P) <0.05 was considered as significant. Statistical analyses will be performed using R software and R Studio (version 4.1.2).

Image omics and model generation methodology

Radiomics Methodology

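### Drug comparisons inside at least 18 subgroups or strata share the primary tests' unadjusted p<0.05 rule, and no interaction test is named to support claims that drug effects differ

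*Protocol*

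**What the plan says.** **Motivation.** The background section on differences between the three drugs says: "Another relevant issue is represented by the potential differential activity of the three molecules across clinical scenarios". After reviewing pivotal-trial results by setting it concludes: "These data suggest a differential activity of the three CDK4/6i drugs in settings that are often encountered during daily clinical practice".

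**Objectives.** The secondary objectives of the RWD sub-study include: "To test the difference in terms of rwPFS, TTNT-D and TTC-D among the three CDK4/6i in clinically-relevant subgroups". Six subgroups are named there: endocrine sensitive, endocrine resistant, premenopausal, poorer ECOG PS, luminal-B like and liver metastases. Separate objectives add OS as a fourth endpoint. Some take a single subgroup, for example "among the three CDK4/6i in patients with lobular breast cancer histology" and "among the three CDK4/6i in patients harboring germline mutations, including" certain genes; women over 75 and carriers of somatic alterations are treated in the same way. Others are worded by factor, for example "among the three CDK4/6i according to disease-free interval (DFI"), and likewise for endocrine resistance status and ER expression level.

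**Decision rule.** Statistical methods states: "All statistical tests will two-tailed, and a p value (P) <0.05 was considered as significant". It names Cox regression, with propensity score matching or inverse probability weighting as options. The protocol contains no interaction term, no multiplicity adjustment and no exploratory label for these objectives.

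**The concern.** Two separate problems follow from this combination.

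1. **Multiplicity.** Dozens of overlapping subgroup tests are declared significant by the same rule as the two primary OS comparisons. Some will cross 0.05 by chance, and the protocol gives no basis for treating those results differently from the primary ones.
2. **Inference about differential activity.** That a drug difference varies between patient types is a statement about interaction. A significant result in one subgroup beside a non-significant result in another does not establish it, because the contrast may reflect only the number of events in each. Several subgroups are listed with no complement, so a test inside them cannot show that activity differs from that in other patients.

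At stake is whether the study reports drug preferences by patient type that come from subgroup size and chance.

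**Working it through.** **1. The protocol's own event figure.** Statistical design gives 977 OS events in 3258 patients for a 20% difference, 80% power and two-sided 0.05. Events by Schoenfeld with 1:1 allocation are 4(1.96+0.84)²/(ln HR)²:
- HR 0.80: 631 (Freedman 636).
- HR 1.20: 945 (Freedman 950). A 41:59 split gives 977.
- HR 0.80 with three equal arms: 1.5 × 636 = 954.

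So 977 can be approached in more than one way, because the hazard ratio scale and drug shares are not stated. I therefore use a range per contrast: 977 × 2/3 ≈ 651 (three equal arms) up to 977. The protocol gives no figure for the subgroup tests.

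**2. Number of subgroup drug tests (low count).**
- Six named subgroups × 3 endpoints = 18 tests.
- Over 75 (1), lobular (1), disease-free interval (2 levels), primary/secondary resistance (2), ER level (2), germline (1), homologous recombination deficiency (1), *PIK3CA* (1), *ESR1* (1) = 12 subgroups or strata × 4 endpoints = 48 tests.
- Total: 18 subgroups or strata and 66 three-drug tests, or 66 × 3 = 198 pairwise tests.

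Two levels per factor is an assumption. If the three objectives worded by factor were each met by an interaction term, 6 × 4 = 24 tests drop out and 42 remain.

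**3. False positives with no true drug difference.**
- Expected: 66 × 0.05 = 3.3; 198 × 0.05 = 9.9; 42 × 0.05 = 2.1.
- At least one among 66 if independent: 1 − 0.95^66 = 0.97. For 42: 1 − 0.95^42 = 0.88.
- The tests are not independent. A simulation of the 66 tests in 3258 patients, with overlapping subgroups of assumed size and equal drug shares, gave 0.87, 0.84 and 0.74 for endpoint correlations of 0.5, 0.7 and 0.9. Pairwise testing gave 0.97-0.99.

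**4. Discordance with a uniform effect.** Take HR 0.80 in every patient and D events in a stratum. Power is approximately Φ(√(D/4) × |ln 0.80| − 1.96). For a subgroup with power p1 and a complement with power p2, P(exactly one significant) = p1(1−p2) + p2(1−p1).

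| Events in contrast | Subgroup share | p1 | p2 | Exactly one significant |
|---|---|---|---|---|
| 651 | 15% | 0.197 | 0.747 | 65% |
| 651 | 30% | 0.345 | 0.663 | 55% |
| 651 | 50% | 0.521 | 0.521 | 50% |
| 977 | 15% | 0.272 | 0.895 | 68% |
| 977 | 30% | 0.480 | 0.831 | 51% |
| 977 | 50% | 0.694 | 0.694 | 43% |

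These are OS-type event numbers. rwPFS, TTNT-D and TTC-D should have more events. Doubling 651 to 1302 as an illustration gives 64%, 42% and 31% for the same three shares, so discordance falls in balanced subgroups but hardly in small ones.

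**5. What interaction tests do and do not achieve.** With a uniform effect, an interaction test signals a difference in 5% of cases, against the percentages above. For two equal strata, the standard error of the log ratio of HRs is √(8/D + 8/D) = √(16/D), with D the total events. For a ratio of 0.80, power is 30% at 651 events and 41% at 977; 80% needs about 2520. One interaction test per factor and endpoint makes 5 × 3 + 9 × 4 = 51 tests, with 51 × 0.05 ≈ 2.6 false positives expected.

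**The case against.** A reader might infer that the sponsor has chosen within-subgroup testing in place of interaction tests. The protocol does not say so. It is silent on interaction, its Cox models do not exclude product terms, the objectives worded by factor could be met by such terms, and the method may stand in an analysis plan that is not shown. This part of the objection stands: the absence of an interaction test is not by itself an error.

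It is also fair that whether the drugs differ in women over 75, or in lobular disease, is a proper question in its own right. The section on real-world data gives the study of under-represented patients as a purpose, and a within-subgroup estimate answers that question. The discordance argument applies only where a subgroup is set against its complement, and in the quoted objective the only explicit pair is endocrine sensitive and resistant.

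The discordance figures rest on OS-type events and equal drug shares, neither of which the protocol states for these endpoints. In the predecessor any-line cohort described in the background, 82.9% received palbociclib. Finally, interaction tests are weak here and do not cure multiplicity.

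What the objection does not remove is the text that the protocol does fix: the objectives are worded as tests, the stated background is differential activity, and one rule calls every p<0.05 significant. An analysis plan that moved these comparisons to an exploratory tier would be changing that rule, not filling in a detail. The false-positive counts do not depend on event numbers.

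**Conclusion.** The point holds as a badly fixed decision rule for secondary objectives. Following the stated rule, about 3 false three-drug subgroup signals are expected among 66 tests (about 10 of 198 pairwise) if the drugs do not differ, with a 74-97% chance of at least one. Spurious findings are therefore likely, but not certain. If the three objectives worded by factor are handled by interaction, the expected number falls to about 2.

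Where a subgroup is read against its complement, a uniform HR of 0.80 gives discordant significance in roughly 43-68% of cases for shares of 15-50% and 651-977 events with equal drug shares. It is less in balanced subgroups for endpoints with more events (about 31% at 1302 events split 50:50).

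A reader might extend the point to the primary analysis. That is not supported: the two primary OS comparisons are unaffected.

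**What to change.** - In Statistical methods, limit the p<0.05 claim rule to the primary comparisons and any secondary comparisons that are explicitly ranked. Label the subgroup drug comparisons exploratory. This carries the multiplicity part of the fix.
- Report subgroup hazard ratios with confidence intervals. Check drug balance, or re-estimate the weights, within each subgroup, because weights estimated on the whole cohort need not balance the drugs inside it.
- Base any statement that drug effects differ between patient types on a drug-by-subgroup interaction term, fitted in the patients with that factor recorded, and not on significance in one subgroup and its absence in another. The restriction matters for genomic factors, which are collected only where tested in clinical practice.
- State the limits: interaction power is about 30-41% for a ratio of HRs of 0.80 with equal strata, and interaction tests do not by themselves control multiplicity.

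**Cost.** A text change and some re-analysis, with no new data. There will be fewer nominally significant subgroup claims, and real differences between patient types of moderate size may go unproven.

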Furthermore, breast cancer intrinsic subtypes, as evaluated by PAM50 transcriptomic profiles, were observed to differently benefit from CDK4/6i in combination with ET. In particular, basal-like tumors are associated with poor prognosis and refractoriness to the addition of CDK4/6i to ET alone, as observed in a retrospective pooled analysis across the MONALEESA phase III studies (mPFS 3.7 with ribociclib vs 3.6 with placebo).^{32,33}

Prognostic biomarkers in HR+/HER2- aBC patients treated with first-line CDK4/6i plus ET combinations

Despite the tremendous improvement in the prognosis of HR+/HER2- aBC patients, a minority (~10-15%) of patients treated with first-line ET+CDK4/6i still undergo early disease progression. This subgroup of patients could therefore benefit from treatment intensification, such as through the addition of a target therapy (e.g., PI3Ki, AKTi, mTORi, PARPi for selected populations), hormonal backbone enhancement (e.g., oral SERD), or even from the use of a completely different treatment strategy such as chemotherapy or novel antibody drug conjugates (ADCs). Conversely, another subgroup of patients demonstrated to derive long-term benefit from ET+CDK4/6i in pivotal trials, with 23.3% of patients enrolled in the MONARCH 3 trial still on treatment after a median follow up of 72 months. These patients could potentially benefit from tailoring treatment in terms of de-escalation, sparing unnecessary toxicities without negatively impacting on survival outcomes.

However, there are no studies conducted to date with the specific aim of identifying the subset of patients at high risk of early progression or, conversely, long-term benefit. Several clinical and biological factors demonstrated in clinical trials to have relevant impact on prognosis, and the addition of specific CDK4/6i differently improved prognosis across pivotal trials. Among these, endocrine resistance, presence of liver metastasis, tumor biology intended as luminal A- or B-like disease, menopausal status, de novo metastatic presentation, patient age and comorbidity.^{37–40} Mason et al conducted an individual-level analysis using

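### The median-imputation rule does not exempt on-treatment blood counts, so patients who fail before T2 can be given an invented T2 change

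*Protocol*

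**What the plan says.** - **Predictor.** In the RWD sub-study, Secondary objectives, the predictor is "blood lymphocyte counts at baseline, or their precocious ontreatment modifications (T1: 2 weeks after treatment initiation, and T2: before fourth cycle initiation", timed as "T2: before fourth cycle initiation, approximately 12 weeks after treatment initiation". The outcomes are rwPFS, TTNT-D, TTC-D and OS. Further objectives do the same for other cell counts, and for NLR, PLR, MLR and PIV against PFS.
- **Model.** Statistical methods: "Multivariable analysis will be performed through Cox regression modeling to estimate the effects of covariates".
- **Missing covariates.** Same section: "Covariates whose values will be missing in less than 20% were imputed by using the median or the mode value", while "covariates with missing values exceeding 20% will be excluded from the present analysis". On-treatment values are not excepted.
- **Missing outcomes.** "Patients with missing outcome data will be excluded from the analysis". An early failure has an outcome; only the T2 count is absent.
- **Three-month exclusion.** The RWD exclusion criteria remove patients with "Less than 3 months of follow up from the CDK4/6i start to the date of data cut-off". Read literally, this runs to data cut-off, so a patient who progressed or died in week 8 but started well before cut-off stays in.
- **Collection times.** The RWD Data collection list places blood counts at baseline, day 15, day 30 and progression. It has no 12-week count. The toxicity sub-study does have a draw before cycle 4, but for liver and kidney parameters.

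**The concern.** Median imputation is meant for baseline covariates with incidental gaps. A T2 change is different: it cannot exist for a patient who failed before T2. Filling it places every early failure at one identical value in the centre of the distribution, so a group defined by its bad outcome enters the model as a block at one covariate value.

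A continuous predictor loses some of its real effect. A predictor cut into groups has the whole block on one side of the cut, and the choice between at-or-above and above the median then decides the sign of the spurious part of the result. What is at stake is the T2 part of the blood-count objectives, which are secondary.

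**Working it through.** The protocol gives no design figure for this objective. Its one sample size, 3258 patients with 977 OS events, belongs to the drug comparison and is used here only as a cohort size.

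**1. Share failing before T2.** T2 is 12 weeks, or 2.76 months. With exponential PFS and median m, the share is 1 - 2^(-2.76/m). The medians are those quoted in the background for first-line patients by HER2 status (32.3 and 23.6 months) and, as a lower value, 13.0 months from the other large cohort described there.

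| m (months) | Before T2 (2.76) | Before T1 (0.46) |
|---|---|---|
| 32.3 | 5.8% | 1.0% |
| 23.6 | 7.8% | 1.3% |
| 13.0 | 13.7% | 2.4% |

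All the T2 shares are below 20%, so early failure alone leads to filling rather than to dropping the variable.

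**2. Mechanism by hand.** Take 2000 patients (the expected number at the first cut-off) and m = 23.6. Then 0.078 × 2000 = 156 fail before T2 and 1844 have a value, 922 on each side of the median. Filling puts all 156 exactly on the cut. If ties count as high, the groups are 922 + 156 = 1078 and 922, and every event before T2 falls in the high group. If ties count as low, the reverse holds.

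**3. Simulation.** Assumptions: exponential PFS, uniform censoring at 3-84 months, standard normal change, univariate Cox model from treatment start, 200-300 runs per setting, early failures given the observed median change.

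No true effect, median split:

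| m | HR, ties high | HR, ties low |
|---|---|---|
| 32.3 | 1.21-1.23 | 0.81-0.82 |
| 23.6 | 1.25-1.27 | 0.79-0.80 |
| 13.0 | 1.38-1.39 | 0.73-0.74 |

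At m = 23.6, false rejection at two-sided 0.05 is about 37% (n = 335), 98-100% (n = 2000) and 100% (n = 3258). Quartile cuts give 1.17 and 0.86, with 87-88% rejection at n = 3258. Adding 10% random missingness (17% missing in total) still gives 1.24 or 0.81.

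For OS, with T2 missing through progression, the HR is 1.21-1.22. Rejection is 21%, 80% and 98% at the same three sizes. This run assumes that 15% of PFS events are deaths and that median post-progression survival is 17.5 months.

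No true effect, continuous change: HR 1.00 with no excess rejection if symmetric; HR 0.97 with 18-22% rejection at n = 2000 or more if right-skewed.

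True HR 0.83 per SD, n = 3258. The figure is the background's first-line T1 result; its unit is not given, so per SD is an assumption.

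| m | Continuous, imputed | High/low, ties high | High/low, ties low |
|---|---|---|---|
| 32.3 | 0.845 | 0.94 | 0.62 |
| 23.6 | 0.848 | 0.97 | 0.61 |
| 13.0 | 0.856 | 1.09 | 0.56 |

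Without imputation the values are 0.83 (continuous) and 0.74 (high/low).

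**4. Which element causes the bias.** A 12-week landmark restricted to observed values gives a high/low HR of 0.99-1.01 and 4-5% rejection with no true effect. A complete-case Cox model from treatment start gives the same HR. Among patients with a T2 value no event precedes T2, so the risk sets at every event time are identical. The time origin shifts the survival curves; the imputation moves the HR.

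**5. Variant.** If the raw T2 count is imputed and the change then computed, there is no false association when neither baseline nor change matters (HR 1.00, 4% rejection). The protocol does not say which quantity would be filled.

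**The case against.** **Landmark handling belongs in an SAP.** This stands. A reader might infer that omitting a landmark is itself the error, but step 4 shows it does not bias the HR. The stated imputation rule is another matter, because the protocol fixes it.

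**No high/low split is prescribed.** This stands too. The earlier study's comparison, described in the background, grouped patients on baseline count together with on-treatment reduction, and its signal was at baseline and two weeks. It is a precedent for grouping, not evidence that T2 will be split. Nor do the documents make T2 change the programme's leading biomarker.

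**The filling may never happen.** Data come from routine records and no 12-week count is on the collection list. At m = 23.6 only 20 - 7.8 = 12.2 percentage points of other missingness are needed before the variable is dropped. That is a fair limit, but dropping it leaves the T2 objective unanswered.

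**The 10-15% early-progression figure.** A reader might take the background's statement that 10-15% "of patients treated with first-line ET+CDK4/6i still undergo early disease progression" as the share failing before T2. In a simulation of 2000 patients, 10% and 15% failing before week 12 give median-split HRs of 1.35 and 1.54. The background gives no time window, so it does not support that use.

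**Covariates may mean only adjustment variables.** The background uses the word that way for the earlier study. Statistical methods, however, applies it to the terms whose effects the Cox model estimates and gives no separate rule for a missing exposure. The text is at best ambiguous.

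**Conclusion.** The concern holds in a limited form. The protocol states one imputation rule for covariates and does not exempt a predictor that is absent because the patient has already failed. With about 6-14% failing before T2, a continuous effect of 0.83 weakens to about 0.85. Any median split would carry a false HR of about 1.2-1.4 or 0.7-0.8, its direction set by the handling of ties.

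This rests on exponential PFS, imputation of the change rather than the raw count, total T2 missingness under 20%, and no other covariates in the model. The large figures apply only if the change is dichotomised. T1 is almost unaffected (1.0-2.4% failing before it), and the primary OS comparison is not touched.

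Separately, the T2 objective and the RWD collection times contradict each other and must be reconciled, because that decides whether T2 values exist in sufficient number.

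**What to change.** 1. In Statistical methods, limit median or mode imputation to baseline covariates and state that T1 and T2 counts, their changes and the derived ratios are never imputed under that rule.
2. Analyse T2 change only in patients who are event-free for the endpoint concerned, in follow-up and with an observed T2 value, counting time from the 12-week landmark. For T1 the exemption is enough.
3. Reconcile the T2 objectives with the RWD Data collection list: add the T2 blood count where routine records hold it, or withdraw the T2 objectives.

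The analysis changes cost wording only. Item 3 may add one data field per patient. The statistical price is that patients failing before T2 leave these secondary analyses, so the result applies only to patients still event-free at about 12 weeks and should be reported that way.
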